9.0 Efficacy Analyses

9.1 General Considerations

All efficacy analyses will be conducted based on ITT2 for Induction Period 1. The overall type I error rate of the primary and secondary endpoints will be strongly controlled using a graphical multiple-testing procedure¹ as described in Section 13.0. Analyses for the efficacy endpoints in Induction Period 2 will be performed based on ITT2_P2.

The primary analysis will be performed after all ongoing subjects have completed the Sub-Study 2 activities up to Week 24 and the Sub-Study 2 database has been locked. This will be the only and final analysis for the primary and secondary efficacy endpoints as well as all additional efficacy endpoints in Sub-Study 2. Treatment assignments will be unblinded to AbbVie for statistical analyses.

Unless otherwise specified, categorical variables will be analyzed using Cochran-Mantel-Haenszel (CMH) test for common risk difference, stratified by Advanced Therapies-IR status (yes vs no), baseline steroid use (yes vs no), and baseline Adapted Mayo score (≤ 7 vs > 7). If there is a stratum for a treatment group that has no subject in it, a value of 0.1 will be added to all cells in the corresponding table in order to prevent dividing by 0, as suggested in Greenland and Robins (1985).³ Greenland and Robins (1985)³ variance estimator is used for the common risk difference. For all stratification factors (including the randomization stratification factors) used for CMH analyses, their values will be based

on actual values. Continuous variables collected longitudinally (more than one post baseline visits) will be analyzed using Mixed-Effect Model Repeat Measurement (MMRM) method. Continuous variables collected with only one post baseline visit will be analyzed using Analysis of Covariance (ANCOVA) model. For multi-level categorical endpoints PGIC, percentage of each outcome category will be reported descriptively, and no statistical comparison will be performed. For time to event analysis, Kaplan-Meier method will be used. For all stratification factors (including the randomization stratification factors) used for analyses, their values will be based on actual values.

Baseline refers to the last non-missing observation on or before the first administration of study drug in Induction Period 1 or randomization if no study drug is given.

9.2 Handling of Missing Data

Missing data could occur due to various reasons, including missing visits/assessments, early withdrawal from the clinical trials, missing due to Coronavirus disease 2019 (COVID-19) infection or logistic restriction, or missing due to geo-political conflict in Ukraine or surrounding area.

The COVID-19 pandemic is interfering with the conduct of many ongoing trials, with potential impacts on treatment duration and the collection, analysis, and the interpretation of clinical trial data. Some protocol-specified visits in the clinical trials may be impacted due to COVID-19 infection or logistical restrictions during the pandemic. For example, some scheduled visits may be missed due to self-quarantine or local government restrictions on travel; some visits may also be delayed or canceled due to healthcare resource constraints during the pandemic. Impacted visits due to COVID-19 will be recorded in the database. The probability of having missed visits and missing data due to COVID-19 infection or logistical restrictions related to the COVID-19 pandemic can be reasonably assumed to be unrelated to the unobserved values. Similarly, the probability of having missed visits and missing data due to geo-political conflict in Ukraine or surrounding area can be reasonably assumed to be unrelated to the unobserved values. Therefore, for the purpose of statistical analysis, it is reasonable to assume that these

missing data are missing at random (MAR) and the statistical models that require MAR assumption are appropriate. The intent is to provide reliable estimates of the treatment effects under the scenario without the impact of COVID-19 pandemic or without the impact of geo-political conflict in Ukraine or surrounding area.

Missing data for the efficacy analyses will be handled using the methods described below.

9.2.1 Categorical Endpoints

For binary efficacy endpoints, missing data will be handled using the following approaches:

- The primary approach for handling missing data in the analysis of binary endpoints except for occurrence of hospitalization and the occurrence of UC-related surgeries will use Non-Responder Imputation while incorporating Multiple Imputation (MI) to handle missing data due to COVID-19 or due to geo-political conflict in Ukraine or surrounding area (NRI-MI).

The NRI-MI will categorize any subject who does not have an evaluation during a pre-specified visit window (either due to missing assessment or due to early withdrawal from the study) as a non-responder for the visit. The only exception is that missing data due to COVID-19 infection or logistical restrictions related to the COVID-19 pandemic or due to geo-political conflict in Ukraine or surrounding area will be handled by Multiple Imputation (MI). At each visit, subjects will be characterized as responders or non-responders based on MI imputed values if missing due to COVID-19 or due to geo-political conflict in Ukraine or surrounding area; otherwise, subjects will be considered as non-responders for missing due to other reasons in the NRI-MI approach. In addition, on or after the date of the UC-related corticosteroids intercurrent event or the occurrence of the UC-related surgery (see Section 8.0), subjects will be counted as non-responders.

- Multiple Imputation (MI) for NRI-MI: Markov Chain Monte Carlo (MCMC) will be first applied to augment data into monotonic missing pattern, where applicable, and PROC MI will be used to generate 30 datasets using the regression method. The variables to be included in

the imputation model are: treatment group, Advanced Therapies-IR status (yes vs no), baseline corticosteroid use (yes vs. no), baseline Adapted Mayo score (≤ 7 vs. > 7), baseline measurement, and if applicable, post-baseline measurements at each visit up to the end of the analysis period. The imputed post-baseline measurements will be rounded to the same precision as the observed data before the determination of responder status.

- When a dichotomized variable is derived from a continuous scale, for example, IBDQ remission (IBDQ total score ≥ 170), the multiple imputation will be applied to the original scale, IBDQ (ranges from 32 – 224) assuming multivariate normal distribution. Then the dichotomized variable will be derived from the imputed value.
- When a dichotomized variable is derived from sub-scales, for example, clinical remission per Adapted Mayo score (SFS ≤ 1 and not greater than Baseline, RBS of 0, and endoscopic subscore ≤ 1), the multiple imputation will be applied to the original sub-scales, SFS, RBS, and endoscopic subscore (all range from 0 – 3). Then the dichotomized variable will be derived from the imputed values.
- For endpoints that are not derived from continuous variables, for example, no bowel urgency, the multiple imputation will be applied to the binary variable directly.

The MI procedure assumes that the data are missing at random (MAR). That is, for an outcome variable Y, the probability that an observation is missing depends only on the observed values of other variables, not on the unobserved values of the outcome variable Y. Statistical inference from the MI procedure is valid under the MAR assumption.

The multiple imputation scenarios are described below:

Scenarios	Argumentation Step	Multiple Imputation Step	PROC MI model
Endpoints that are derived from continuous scale or sub-scales and planned to have multiple post-baseline visits	Markov Chain Monte Carlo (MCMC) will be first applied to augment data into monotonic missing pattern.	For each monotone missing dataset, using SAS PROC MI with MONOTONE REG model statement, the outcome variable at each post-baseline visit with missing values will be imputed sequentially with covariates constructed from their corresponding sets of preceding variables	The imputation model for the missing data is a regression model, which controls for treatment group, Advanced Therapy-IR status (yes vs no), baseline corticosteroid use (yes vs. no) and baseline Adapted Mayo score (≤ 7 vs. > 7 (per central read after adjudication, when applicable), baseline measurement, and if applicable, post-baseline measurements at each visit up to the end of the analysis period.
Endpoints that are derived from continuous scale or sub-scales and have only single post-baseline	N.A.	PROC MI with FCS REG will be used	
Endpoint that are not derived from continuous variable	N.A.	PROC MI with FCS LOGISTIC will be used	

A 'complete' dataset with imputed values for the missing data is generated after the augmentation and imputation steps are completed.

- Subjects will then be characterized as responders or non-responders based on MI imputed datasets. Using the CMH model adjusted by stratification factors (Advanced Therapies-IR status (yes vs no), baseline steroid use (yes vs no), and baseline Adapted Mayo score (≤ 7 vs > 7)), the imputed endpoints will be analyzed using each of the 30 datasets. SAS PROC MIANALYZE will be used to generate the final inferences of the risk difference between risankizumab treatment group and placebo group, using Rubin's rule. Note that measurements will be set to missing on or after the date of the UC-related corticosteroids intercurrent event or the occurrence of the UC-related surgery before applying MI. After the MI imputation, an NRI override will be implemented for missing values 1) due to reasons other than COVID-19 infection or logistic reasons or geo-political conflict in Ukraine or surrounding area, or 2) on or after the date of the UC-related corticosteroids intercurrent event, or 3) on or after or the date of the

UC-related surgery intercurrent event. That is, regardless of MI imputed values, subjects satisfying 1) or 2) will be considered as "non-responder" for binary efficacy endpoints.

- For binary efficacy endpoints of occurrence of hospitalization and the occurrence of UC-related surgeries, As Observed (AO) analysis will be used.
 - As Observed: The AO analysis will not impute values for missing evaluations, and thus a subject who does not have an evaluation on a scheduled visit will be excluded from the AO analysis for that visit. AO will include all values collected in the study regardless of intercurrent events.
- Tipping Point Analysis for Binary Endpoints
 - The tipping point analyses are two-dimensional, i.e., assumptions about the missing outcomes on each of the risankizumab group and the placebo group can vary independently. The response rate among those subjects with missing response is assumed to be p_0 for placebo group and p_1 for risankizumab group, and the response rate p_0 and p_1 systematically vary from 0% to 100% by every 10% respectively. Given a set of (p_0, p_1) , the subjects with missing response will be randomly assigned as responders or non-responders using binomial distribution to generate 30 imputed datasets, and the same CMH method used for the primary analysis will be performed on each of the imputed datasets to obtain the results for each comparison between the risankizumab group versus the placebo group. SAS PROC MIANALYZE will be used to generate the final inferences of the risk difference between risankizumab group and placebo group, using Rubin's rule.⁴
 - If one pair of (p_0, p_1) is found to reverse the study result interpretation in terms of p-value larger than 0.05, then the (p_0, p_1) is identified as the tipping point. The results for a grid of (p_0, p_1) combinations are provided in tabular format. Note that missing data on or after the date of the UC-related corticosteroids intercurrent event or on or after or the date of the UC-related surgery will be considered as non-responders and will not be imputed in the tipping point analysis.

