9.6 Efficacy Subgroup Analyses

Subgroup analysis will be performed for the primary efficacy endpoint for the subgroups listed in Table 3 below using ITT2. Point estimate and 95% CI for each treatment group as well as point estimate and 95% CI for treatment differences between risankizumab 1200 mg IV and placebo groups will be presented. The NRI-MI approach will be used for missing data handling. No p-value will be provided. If any of the resulting subgroups except for age, sex and race has fewer than 10% of the planned study size, the subgroup analyses for that category will not be presented.

Table 3. Subgroups for Efficacy Analysis

Subgroup Factor	Categories
Age	[18, 40), [40, 65), ≥ 65
Sex	Male or Female
Baseline weight	< 60 kg or ≥ 60 kg
Race	White or non-White
Geographic Region	North America, South/Central America, Western Europe, Eastern Europe, Asia, Other
Baseline corticosteroid use	Yes or No
Baseline immunosuppressant use	Yes or No
Baseline Adapted Mayo Score	≤ 7 or > 7
Baseline Partial Adapted Mayo Score	≤ 4 or > 4
Prior exposure to anti-TNF for UC for non-Advanced Therapy-IR population	Yes or No
Number of prior failed anti-TNF for UC for Advanced Therapy -IR population	0, 1, 2, > 2
Prior exposure to advanced therapy	0, 1, > 1
Number of prior failed advanced therapies	0 (Non-Advanced Therapy -IR population), ≥ 1 (Advanced Therapy -IR population) (Then analyze 1, 2, > 2 within Advanced Therapy -IR population)
Presence of pancolitis at Baseline	Yes or No
Disease Duration at Baseline	\leq median or $>$ median
Disease Duration at Baseline	\leq 3 years or $>$ 3 years
Baseline hs-CRP	\leq median or $>$ median
Baseline hs-CRP	\leq 5 mg/L or $>$ 5 mg/L
Baseline Albumin	\leq median or $>$ median
Baseline Calprotectin	\leq median or $>$ median
Baseline Calprotectin	\leq 250 mg/kg or $>$ 250 mg/kg

All the secondary efficacy endpoints will be analyzed in the Advanced Therapy-IR and non-Advanced Therapy -IR subgroups in the ITT2 population.

In addition, point estimate of response rate will be summarized for primary endpoint for the following subgroups based on ITT2 population using NRI-MI for risankizumab treatment group (risankizumab 1200 mg IV):

- Treatment Emergent Anti-Drug Antibodies (ADA+, ADA-)
- Treatment Emergent NAb status (NAb+, NAb-)

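### The NRI-MI imputation models leave out geographic region, although location largely governs who can have conflict-related missing data; the likely bias is small and adding the variable costs almost nothing

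*SAP*

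**What the plan says.** SAP 9.2 (Sub-Study 2) sends two kinds of missing data to multiple imputation: those due to COVID-19 and those due to the conflict in Ukraine or nearby. Other missing binary outcomes count as non-response. The justification is that the probability of "missing data due to geo-political conflict in Ukraine or surrounding area can be reasonably assumed to be unrelated to the unobserved values", and hence that these "missing data are missing at random (MAR) and the statistical models that require MAR assumption are appropriate". Section 9.2.1 defines MAR to mean that "the probability that an observation is missing depends only on the observed values of other variables".

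The predictors are listed in the text of 9.2.1: "the imputation model are: treatment group, Advanced Therapies-IR status (yes vs no), baseline corticosteroid use (yes vs. no), baseline Adapted Mayo score" (two categories), then "baseline measurement, and if applicable, post-baseline measurements at each visit up to the end of the analysis period". The scenario table repeats the list. Neither place has a region or country term. For outcomes with a single post-baseline visit the table says "PROC MI with FCS REG will be used".

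Region is available. Appendix E allocates countries to regions and places Ukraine in Eastern Europe. Table 3 in 9.6 uses the categories "North America, South/Central America, Western Europe, Eastern Europe, Asia, Other" for a subgroup analysis of the primary endpoint, itself under NRI-MI.

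Section 9.3.3 adds three analyses that bear on the imputed subjects: a tipping-point grid (each arm from 0% to 100% in steps of 10%), an as-observed analysis, and a rerun without conflict-impacted subjects. All three are specified for the primary endpoint only.

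**The concern.** Conflict-related missingness arises almost entirely in one part of the world. If remission differs there in ways that prior treatment failure, steroid use, baseline severity and the subject's own measurements do not explain, then missingness is related to the unobserved outcome through location. MAR can then hold only if the model conditions on location, and this one does not. Imputed values for affected subjects are drawn toward a fit to which other regions also contribute.

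The Week 12 endoscopic subscore is the most exposed component:

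- Protocol Appendix C schedules endoscopy in Period 1 only at Screening and Week 12, so no earlier post-baseline value can inform the imputation.
- Inclusion criterion 3 restricts the baseline subscore to 2 or 3, so the baseline value says little.
- The SAP does not say whether stool frequency (SFS) and rectal bleeding (RBS) subscores enter the endoscopy model.
- Protocol 5.3.1.1 names endoscopy as an assessment the conflict may prevent.

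This subscore feeds the primary endpoint and five of the first ten secondary endpoints: clinical response per Adapted Mayo, endoscopic improvement, HEMI, endoscopic remission and HEMR.

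**Working it through.** **1. The plan's own figure.** SAP 2.4 assumes 16% vs 6% with 644:322 subjects, two-sided 0.05, and claims at least 90% power. A normal-approximation calculation and a simulated Miettinen-Nurminen test both give 99.8%; 90% power would need 156 placebo subjects. The claim is correct. It does not depend on the imputation model.

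**2. When the risk difference (RD) is biased.** Let m be the share of each arm missing for the conflict, with all of them in the affected region. Suppose, as an upper-end case, that no other predictor helps and missing subjects are imputed at the observed pooled arm rates. Then

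bias = m × (RD observed − RD in region).

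Treatment group is in the model, so a regional shift that is equal in both arms on the risk-difference scale cancels. With 16% vs 6% elsewhere and 22% vs 12% in the region, both differences are 10 points and the bias is 0.

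**3. Size under assumed regional rates.** The documents give neither m nor regional rates; both are assumptions. Fix the overall true RD at 10. For a region with 13% vs 8% (RD 5), the observed RD is (10 − 5m)/(1 − m):

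| m | Observed RD | Bias (points) |
|---|---|---|
| 3% | 9.85/0.97 = 10.15 | +0.15 |
| 5% | 9.75/0.95 = 10.26 | +0.26 |
| 10% | 9.50/0.90 = 10.56 | +0.56 |

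A region with 20% vs 5% (RD 15) gives the same sizes with a negative sign.

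The planning standard error is √(0.16×0.84/644 + 0.06×0.94/322) = 1.96 points, so these biases are about 0.08 to 0.28 standard errors.

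**4. A harsher case.** Fix the rest of the trial at 16% vs 6% and let the region have no effect (16% vs 16%). The bias is m × 10, or 0.1, 0.2, 0.5 and 1.0 points at m = 1%, 2%, 5% and 10%. At m = 10% the true overall rates are 16% and 0.9×6 + 0.1×16 = 7%, a difference of 9 points; power there is 98.7%.

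**5. Effect of the subject's own earlier data.** Regression imputation of a latent Week 12 score was simulated with 400 trials per scenario, 10% of subjects in the region, half of those missing, and an early measurement correlated 0.7 with Week 12. Shifts are in latent standard deviations; entries are RD bias in points.

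| Regional shift (placebo, risankizumab) | No early value, no region | Early value, no region | Early value, region and region-by-arm |
|---|---|---|---|
| 0.4, 0.4 | −0.27 | −0.09 | −0.04 |
| 0.4, 0 | +0.27 | +0.07 | −0.08 |
| −0.4, −0.4 | +0.21 | +0.06 | 0.00 |
| 0.6, 0 | +0.52 | +0.18 | −0.03 |

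The first column is closest to endoscopy if SFS and RBS do not enter its model; the second is closest to SFS and RBS. An equal shift on the latent scale still gives some bias, because it is not equal on the risk-difference scale.

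**6. The regional subgroup.** Assume the region is 20% of each arm, 5% of each arm is missing (all in the region), and the rates are 13% vs 8%. Then 5/20 = 25% of regional subjects are imputed. The subgroup RD becomes 0.75×5 + 0.25×10.26 = 6.3 against a true 5, an overstatement of about 1.3 points.

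**The case against.** A reader might infer that conflict-region subjects simply receive the remission rates of the rest of the trial. The documents do not support that. Imputation conditions on arm, the three prognostic factors, the baseline value and, for SFS and RBS, the Week 4 and Week 8 values. Observed subjects from the same region also inform the fit. Remission needs all three components, so an observed Week 12 SFS above 1 or RBS above 0 settles the outcome whatever endoscopy value is imputed. The step 3 figures are therefore near an upper bound for the assumed rates.

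A reader might also infer that MAR fails outright, or that location alone decides who is missing. Neither follows. MAR fails only if outcomes differ by region after the listed predictors, and the documents offer no evidence of that. Listing region in Table 3 is not evidence: sex, race and albumin are listed there too and are also absent from the model. Location is close to necessary for conflict-related missingness but not sufficient, and COVID-19 gaps from any region pass through the same imputation.

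The predictors match the CMH stratification factors, a conventional choice. For the primary endpoint, the tipping-point grid spans every regional rate assumed above, and the exclusion analysis tests dependence on conflict-impacted subjects.

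All of this stands. What it leaves open is narrower. None of the planned analyses re-imputes with region. The tipping-point grid is not region-specific, and the exclusion analysis changes the population. No counterpart is specified for the NRI-MI secondary endpoints or for the regional subgroup. Even a shift that cancels in the risk difference still moves the arm-specific rates that SAP 9.3.2 reports.

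**Conclusion.** The omission is real and worth correcting, but its effect is modest. Under the assumed regional rates and 3% to 10% of each arm missing, the overall risk difference moves by about 0.2 to 0.6 points in either direction. It moves less where the subject's own Week 4 and Week 8 values are used (0.06 to 0.18 points in the simulation). With no treatment effect at all in the region and 10% missing, it reaches 1.0 point. These sizes rest on regional rates, missing shares and an early-to-late correlation that the documents do not supply.

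It would be a mistake to conclude that the primary result is in doubt: power stays near 99% even in the harsher case, and SAP 9.3.3 already tests that endpoint. The point carries more weight for the endoscopy-based secondary endpoints under type I error control and for the regional subgroup estimate.

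**What to change.** In SAP 9.2.1, in both the text and the scenario table, add a binary region variable as a main effect to every NRI-MI imputation model. It can be Eastern Europe vs other per Appendix E, or a list of conflict-affected countries fixed before unblinding. Report the numbers imputed by arm and region.

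Keep any treatment-by-region term to a pre-specified sensitivity analysis. If the region were 20% of placebo, it would hold about 0.2×322 = 64 subjects and, at 6%, about 4 remitters, too few for a stable interaction in the primary model. A main effect absorbs a regional shift common to both arms on the imputation scale, but not a genuine regional difference in treatment effect. The sensitivity analysis is there for that, and the simulation above fitted region together with region-by-arm, not the main effect alone.

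The cost is one variable already defined, with no new data or subjects. Imputations become slightly more variable in sparse cells. Eastern Europe, which covers 18 countries in Appendix E, is a broad proxy for exposure to the conflict, and neither choice of variable captures country differences in COVID-19 restrictions.

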3.0 Endpoints

Below are the endpoint definitions for efficacy variables:

- Mayo Score
 - Full Mayo Score: composite score of UC disease activity based on the
 - stool frequency subscore [SFS] (0 – 3), rectal bleeding subscore [RBS] (0 – 3), physician's global assessment [PGA] subscore (0 – 3) and endoscopic subscore (0 – 3). The endoscopic subscore will be based on central readings after adjudication (when applicable). The Full Mayo score ranges from 0 – 12 points with higher scores representing more severe disease.
 - Partial Mayo Score: Full Mayo score excluding the endoscopic subscore.
 - Adapted Mayo Score: Full Mayo score excluding the PGA subscore.
 - Partial Adapted Mayo Score: Adapted Mayo score excluding the endoscopic subscore.
- Clinical Remission per Adapted Mayo: stool frequency subscore (SFS) ≤ 1 , and not greater than baseline, rectal bleeding subscore (RBS) = 0, and endoscopic subscore ≤ 1 without the evidence of friability
- Clinical Response per Adapted Mayo: decrease from Baseline ≥ 2 points and $\geq 30\%$, PLUS a decrease in RBS ≥ 1 or an absolute RBS ≤ 1
- Clinical Response per Partial Adapted Mayo (without endoscopy): decrease from Baseline ≥ 1 points and $\geq 30\%$, PLUS a decrease in RBS ≥ 1 or an absolute RBS ≤ 1
- Clinical Remission per Full Mayo: Full Mayo score ≤ 2 with no subscore > 1

- Endoscopic Improvement: endoscopy subscore of 0 or 1 without the evidence of friability
- Endoscopic Remission: endoscopic subscore = 0
- Histologic Remission: Geboes score of < 2.0
- Histologic Endoscopic Mucosal Improvement (HEMI): Endoscopic subscore of 0 or 1 without the evidence of friability and Geboes score \leq 3.1.
- Histologic Endoscopic Mucosal Remission (HEMR): Endoscopy subscore of 0 and Geboes score < 2.0

Note: Evidence of friability during endoscopy in subjects with otherwise "mild" endoscopic activity will confer an endoscopic subscore of 2.

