- Note: The stool frequency subscore during days which the subject received anti-diarrheal medication will be scored as a 3.
- Define a 10-day period during which daily subscores are collected before the partial adapted Mayo score at each visit.
- Subscores will be calculated by averaging the 3 most recent valid Daily SFS & RBS within the 10-day period, excluding the day before endoscopy (due to bowel preparation), day of endoscopy and 2 days following the endoscopy (for visits that include an endoscopy). The calculated scores following these above rules will be recorded to an eCRF page by study sites that will be used in the primary analysis.

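### Normal-regression imputation of the Mayo subscores (SAP 9.2.1) produces remission too rarely when Week 12 rectal bleeding is missing for COVID or conflict reasons; the effect on the primary estimate is small

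*SAP*

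**What the plan says.** The primary missing-data method for the primary endpoint is non-responder imputation, with multiple imputation only for data missing because of COVID-19 or the conflict in Ukraine and the surrounding area (SAP, Sub-Study 2, Sections 9.2.1 and 9.3.2). For remission per Adapted Mayo score, "the multiple imputation will be applied to the original sub-scales, SFS, RBS, and endoscopic subscore (all range from 0 – 3"), and remission is derived from the imputed values.

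- **Model.** Scales with several post-baseline visits are imputed "using SAS PROC MI with MONOTONE REG model statement"; for those with a single post-baseline visit, "PROC MI with FCS REG will be used". For endpoints not derived from a continuous variable, "PROC MI with FCS LOGISTIC will be used".
- **Rounding.** "The imputed post-baseline measurements will be rounded to the same precision as the observed data before the determination of responder status". No rounding unit, lower bound or truncation rule is given, and the text does not say whether the three subscores inform each other.
- **Observed scores.** Section 9.3.2: "Subscores will be calculated by averaging the 3 most recent valid Daily SFS & RBS within the 10-day period". The result "will be recorded to an eCRF page by study sites" and feeds the primary analysis.
- **Endpoint.** Section 3.0 requires RBS equal to 0, together with limits on stool frequency (SFS) and endoscopy.

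Section 9.2 states the aim: reliable estimates of the treatment effect as if neither the pandemic nor the conflict had intervened.

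**The concern.** RBS has a point mass at 0, and remission depends on hitting it. A normal draw has no such mass. Rounded on a fine grid it seldom lands on 0, and a draw below zero fails the criterion although it lies on the favourable side: read literally, −0.4 rounds to −1/3, which is not 0. The imputed remission rate is then too low in each arm. This loss comes from the form of the imputation model, so it arises even when the missing-at-random assumption in Section 9.2.1 holds.

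Active treatment has more remitters to lose. With similar missing shares the risk difference is therefore pulled towards zero, and the imputation step does not deliver what Section 9.2 intends. Because the rounding unit and the handling of negative draws are unstated, two programmers could also obtain different primary results from the same data.

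**Working it through.** **1. Inputs and the plan's own figure.** SAP 2.4 gives remission of 6% on placebo and 16% on risankizumab, 322 and 644 subjects, two-sided alpha 0.05 and power of at least 90%. Pooled rate = (644 × 0.16 + 322 × 0.06)/966 = 0.1267. Null SE = √(0.1267 × 0.8733 × (1/644 + 1/322)) = 0.0227. Alternative SE = √(0.16 × 0.84/644 + 0.06 × 0.94/322) = 0.0196, or 1.96 points. Power = Φ((0.10 − 1.96 × 0.0227)/0.0196) = 99.8%. The plan's lower bound holds.

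**2. One draw.** For a rounding unit u and a predictive mean m and SD s, the chance of an imputed 0 is Φ((u/2 − m)/s) − Φ((−u/2 − m)/s). With assumed m = s = 0.5:
- thirds: 0.252 − 0.091 = 0.161, with a further 0.091 lost below the zero band;
- two decimals: about 0.005;
- whole points: 0.500 − 0.023 = 0.477.

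**3. Simulation.** The score distributions are assumptions. Trials of 644:322 were calibrated to about 16% and 6% remission, with RBS and SFS as means of three daily scores. 10% of Week 12 values were deleted at random and imputed by Bayesian normal regression. One scenario (RBS = 0 in about 28% placebo and 51% active, all three subscores missing, subscores informing each other; true remission among those deleted 6.2% and 16.0%):

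| Rounding | Bounds | Imputed placebo | Imputed active | Bias in difference, points × share |
|---|---|---|---|---|
| thirds | none | 1.4% | 3.9% | −7.3 |
| thirds | clipped to 0–3 | 3.7% | 10.9% | −2.7 |
| 0.01 | none | 0.1% | 0.1% | −9.8 |
| 0.01 | clipped to 0–3 | 2.8% | 7.8% | −4.8 |
| whole points | clipped to 0–3 | 6.8% | 16.9% | +0.2 |

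The first row follows as (3.9 − 1.4) − (16.0 − 6.2) = −7.3. Across three assumed RBS distributions and both joint and separate models, with RBS missing and sub-integer rounding, the bias was −4.8 to −11.7 points × share unbounded and −0.6 to −7.9 clipped. Values beyond −10 arise because the simulated true difference among the deleted cases exceeded 10. Whole points with clipping gave −3.3 to +3.3.

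**4. Endoscopy alone missing.** The RBS mechanism is absent. In the same scenario the bias was −0.1 points × share when observed Week 12 SFS and RBS informed the endoscopy model, and −6.1 when they did not. A second set of four assumed distributions gave −2.6 to −1.0 and −5.5 to −4.0.

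**5. Ceiling for the trial.** If no imputed subject remits, the loss is 16 × f1 − 6 × f0 points.
- Equal shares of 2%, 5% and 10%: 0.2, 0.5 and 1.0 points.
- f1 = 5%, f0 = 2%: 0.80 − 0.12 = 0.68 points. The overall share is (644 × 0.05 + 322 × 0.02)/966 = 4%, so share × 10 would give only 0.40.
- f1 = 3%, f0 = 9%: 0.48 − 0.54 = −0.06, so the difference is slightly overstated. In this limit the sign turns at f0/f1 = 16/6 = 2.7.

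**6. Power at the ceiling.** At 10% missing the rates become 14.4% and 5.4%, and the formula in step 1 gives 99.4%. At 2% and 5% it gives 99.7% and 99.6%.

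**7. Alternative.** Predictive mean matching left −1.1 to +0.1 points × share with all subscores missing in the four-distribution simulation (Monte Carlo error about 0.4). Joint normal regression at thirds left −8.1 to −7.1 unbounded and −4.8 to −2.9 clipped. In a separate check on RBS alone, RBS = 0 truly occurred in 27–46% of active subjects. Unbounded regression at thirds gave 9–14%, and matching gave 26–46%.

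**The case against.** The strongest reply is that the affected pattern is narrow. The loss that the documents plan for is a missing endoscopy (SAP 2.2; Protocol 5.3.1.1). SFS and RBS come from a daily electronic diary (Protocol 10.3), virtual visits are allowed, and premature-discontinuation procedures are due within two weeks of the last dose (Protocol 5.4.1). This stands as a limit on scope. It does not remove the point: SAP 5.0 lists discontinuation from study for COVID-19 and geo-political reasons, and the primary analysis uses scores entered by sites at visits. A missed visit might therefore lose RBS even where diary entries exist, but that is an inference.

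Second, the SAP states no rounding unit, and whole-point rounding with clipping would leave a small bias of either sign. That is correct. Averaging over three days makes a finer unit the more natural reading, but the direction of bias depends on it.

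Third, safeguards exist. The tipping-point grid varies the response rate in each arm from 0% to 100%, and Section 9.3.3 adds an as-observed analysis and one excluding conflict-affected subjects. These test robustness. None corrects the primary estimate: the as-observed analysis ignores intercurrent events, and the exclusion analysis still imputes COVID-related data the same way.

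A reader might infer that the bias never exceeds the missing share times 10 points. That holds only for equal shares. A reader might also infer that the primary test is endangered. The documents do not support that: the worst case is the non-responder rule that the SAP already applies to all other missing data, and with similar shares it is conservative.

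**Conclusion.** The point holds, with conditions. If Week 12 RBS is missing for COVID or conflict reasons and the rounding unit is finer than a whole point, the stated method imputes remission too rarely in both arms, even under missing at random. With equal shares the risk difference loses at most the share times 10 points, about half a standard error at 10% missing; the general ceiling is 16 × f1 − 6 × f0. The effect on power is negligible.

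This rests on the planning rates, on assumed missing shares and score distributions (neither is in the documents), and on reading the precision as fractional. Strongly unequal shares are not expected from these causes under blinding, but could reverse the sign. The change is worth making but optional.

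**What to change.** In SAP 9.2.1, replace REG by predictive mean matching (REGPMM) for the Mayo subscores, and impute SFS, RBS and the endoscopic subscore jointly, each informing the others. Imputed values then stay on the observed 0–3 grid, and remission and clinical response are still derived from the same imputed subscores.

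If REG is kept, state the rounding unit, that the subscores inform each other, and that negative draws are set to 0 after imputation. This reduces the bias but does not remove it.

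Imputing remission directly by the logistic option already in the SAP table is not advised, because it separates remission from response. Remission means an Adapted Mayo score of at most 2 from a baseline of 5–9, so every remitter is a responder. Without an added consistency rule, logistic imputation made 1.3–1.9% of active and 0.9–1.4% of placebo missing subjects remitters but non-responders in simulation.

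The cost is SAP wording, slightly more programming and a small residual bias from matching. No new data are needed.
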